4.3 Schedule of Assessments

[figure not shown]
Table 4-1 Schedule of Assessments

Part 1

[figure not shown]

[figure not shown]

[figure not shown]

[figure not shown]
Part 2

[figure not shown]

[figure not shown]

5. Statistical Methodology and Study Endpoints

5.1 Statistical Methods Planned in the Protocol and Determination of Sample Size

This SAP will be approved prior to database lock. The SAP expands the statistical section of the protocol and contains a detailed description of methods to analyze data collected in the study. The text portion of the SAP will be included in the CSR report as Appendix 16.1.9. Information on the PK, PK/PD, pharmacogenetic, and biomarkers analyses can be found in the PK data analysis plan. Information regarding health economics and outcomes research are found in a separate SAP.

5.1.1 Statistical and Analytical Plans

Statistical analyses will be conducted using SAS Version 9.4 or newer.

5.1.1.1 Common Conventions

5.1.1.1.1 Analysis Populations

The analysis populations will consist of subjects as defined below:

Table 5-1 Analysis Populations

Population	Definition	Study Treatment
Screened	All screened subjects who sign informed consent.	—
Intent-to-Treat (ITT)	All randomized subjects will be included in the randomly assigned treatment group, even if they receive a different treatment from that to which they are randomly assigned. This will be a supportive analysis set for selected efficacy analyses. Subjects with missing Screening biopsy data should not be randomized in the study, and hence will not be included in the ITT analysis set, should such subjects exist.	Randomized assignment
Modified Intent-to-Treat (mITT)	All randomized subjects who receive ≥ 1 dose of study drug will be included in the randomly assigned treatment group, even if they receive a different treatment from that to which they are randomly assigned. This will be the primary analysis set for the efficacy analyses.	Randomized assignment
Month 12 per protocol (PP1)	All subjects randomly assigned to a treatment group who have an evaluable biopsy at Screening and another after at least 6 months but before 15 months of follow-up, receive at least 6 months of assigned study drug and have no significant protocol deviations that potentially influence the primary efficacy assessment will be included in the PP1 analysis set. This will be a supportive analysis set for selected efficacy analyses of Part 1 and Part 2.	Randomized assignment

Population	Definition	Study Treatment
Month 60 per protocol (PP2)	
All subjects randomly assigned to a treatment group who have an evaluable biopsy at Screening, have no significant protocol deviations that potentially influence the primary efficacy assessment, and either:
 
 • Have an adjudicated event that is a component of the primary composite endpoint within 24 months after randomization 
OR
 
 • Have at least 24 months of follow-up for clinical events AND one of the following: 
 • Have an adjudicated event that is a component of the primary composite endpoint within 6 months of last intake of study drug 
OR
 
 • Have a biopsy at least 24 months after randomization and within 6 months of last intake of study drug. 
This will be a supportive analysis set for selected efficacy analyses of Part 2.
	Randomized assignment
Safety	
All subjects who received ≥ 1 dose of study drug will be included in the safety analysis set. Subjects will be included in the treatment group according to actual treatment received, even if they receive a different treatment than that to which they are randomly assigned. Subjects who inadvertently receive both treatments will be included with the CVC group.
 
This will be the primary analysis set for the safety analyses.
	Actual received ¹
Pharmacokinetic	All subjects who are randomized and receive at least one dose of study drug and have at least one post-dose PK sample will be included in the PK analysis set.	Randomized assignment

¹ Subjects will be summarized according to the study treatment received.

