### **9.3. Study Drug Administration**

Subjects will take 1 tablet of study drug daily for approximately 6 to 8 years of treatment.

Subjects will be instructed to take their medication (CVC or placebo) with food.

If a subject has missed a dose of study drug and is still within 12 hours of the time it is usually taken, the subject should take a dose of the missed drug as soon as possible, with food. The subject may then continue the usual dosing schedule. If the subject has missed a dose of study drug more than 12 hours after the time it is usually taken, the subject should not take the missed dose and should resume the usual dosing at the next scheduled time. The subject should not take a double dose to make up for a missed dose or take more than 1 tablet within 12 hours.

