### **11.2. Assessments of Efficacy**

In Part 1, subjects meeting all eligibility criteria and with suspicion of significant liver fibrosis (through clinical, hepatic fibrosis indices, and/or liver stiffness assessment) will have a liver biopsy read by an independent central pathologist during the Screening period. In randomized subjects, a second post-treatment liver biopsy will be collected within  $\pm 2$  weeks of the Month 12 visit.

In Part 2, newly enrolled subjects will undergo a liver biopsy at Screening for assessment of eligibility and a second post-treatment liver biopsy will be collected within  $\pm 2$  weeks of the

Month 12 visit. All subjects (newly randomized subjects with a liver biopsy diagnosis of NASH and Stage 3 liver fibrosis (by NASH CRN system) and those who continue from Part 1) will undergo a liver biopsy at Month 60 (within  $\pm$  2 weeks) after first dose of study drug.

At the end of study, if a subject has received study drug for at least 6 months and has not had the Month 60 biopsy, then a biopsy should be taken within 30 days of the end of study, if feasible.

Liver biopsies will be performed per standard of care (eg, taking into account the subject's health status, coagulation profile, and use of concomitant medications). Subjects who discontinue study drug are encouraged to continue with all other evaluations as scheduled in this protocol, including biopsies and other invasive procedures at the scheduled visits. If a subject discontinues study participation early and has received study drug for at least 6 months in Part 1 or Part 2, then a biopsy should be taken within 30 days of discontinuation, if feasible. All liver biopsies will be evaluated by an independent central pathologist; whenever possible, the same pathologist will evaluate all biopsies from an individual subject. The independent central pathologists will be blinded to individual treatment assignment.

Liver biopsy at Screening and Months 12 and 60 will be used to determine improvement in histologic fibrosis stage (NASH CRN – the system used to assess the primary efficacy endpoint – and Ishak systems).

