Newly randomized subjects in Part 2 will undergo a liver biopsy at Screening for assessment of eligibility and a further liver biopsy at Month 12 (within ± 2 weeks). All subjects in Part 2 will undergo a liver biopsy at Month 60 (within ± 2 weeks) after the first dose of study drug.

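### If last intake means the final dose, the Month 60 per-protocol set keeps nearly all subjects with events but drops most event-free completers, which pulls its hazard ratio towards 1

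*SAP*

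**What the plan says.** **Membership.** SAP Table 5-1 and Protocol 12.1.1 define PP2 alike. Every member needs an evaluable Screening biopsy and must "have no significant protocol deviations that potentially influence the primary efficacy assessment". Beyond that there are three routes in:

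1. "Have an adjudicated event that is a component of the primary composite endpoint within 24 months after randomization".
2. With at least 24 months of follow-up: "Have an adjudicated event that is a component of the primary composite endpoint within 6 months of last intake of study drug".
3. With at least 24 months of follow-up: "Have a biopsy at least 24 months after randomization and within 6 months of last intake of study drug".

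Only route 3 is open to a subject without an event. The PP2 definition does not say which dose counts as the last intake.

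**Biopsies.** SAP 4.1.1 sets the last scheduled biopsy: "All subjects in Part 2 will undergo a liver biopsy at Month 60". Protocol 11.2 adds that if a subject with at least 6 months of drug "has not had the Month 60 biopsy, then a biopsy should be taken within 30 days of the end of study, if feasible". It also asks for an exit biopsy within 30 days, where feasible, from subjects who leave the study early after at least 6 months of drug.

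**Dosing.** Protocol 9.3: "Subjects will take 1 tablet of study drug daily for approximately 6 to 8 years of treatment". The Synopsis estimates 60 months but says that the actual duration depends on reaching 367 subjects with events. SAP 5.1.2 gives 2 years of accrual, about 8 years in total, and 5 to 6 years of follow-up. The Part 2 imputation model in SAP Table 5-4 uses horizons of 96 and 84 months.

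**Role.** Protocol 12.3.2.2 makes mITT primary for Part 2 and PP2 supportive. It also reports the Part 2 secondary endpoints in PP2.

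**The concern.** The routes treat subjects with and without events differently. Under Protocol 7.1, a subject who reaches cirrhosis or a liver-related outcome completes the study, so event and final dose lie close together and route 1 or 2 is easily met. An event-free subject keeps taking drug until the event-driven end, while the last scheduled biopsy stays at Month 60. A subject who takes every dose and has every scheduled biopsy can therefore fail the Month 60 per-protocol set.

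The arms differ mainly in how many subjects have an event. A set from which most event-free subjects are gone has lost that information, and its hazard ratio moves towards 1 even when the drug works. Such an analysis can neither corroborate nor challenge the mITT result. The Month 60 fibrosis endpoints reported in PP2 would likewise leave out most adherent event-free subjects.

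**Working it through.** **Inputs** (SAP 5.1.2): placebo 80% event-free at Month 60, hazard ratio 0.62, 2000 subjects allocated 2:1, 24 months of accrual, 367 events, 20% dropout.

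**The plan's own figures.**
- Placebo hazard = -ln(0.80)/60 = 0.00372 per month. Medians: ln 2/0.00372 = 186 months (15.5 years), and 15.5/0.62 = 25.1 years. The plan says 15 and 25.
- Schoenfeld power: sqrt(367 × 2/3 × 1/3) × |ln 0.62| = 9.03 × 0.478 = 4.32. At two-sided 0.00125, 4.32 - 3.23 = 1.09, giving 86.2% (plan 85%). At 0.05, 4.32 - 1.96 = 2.36, giving 99.1% (plan 99%).
- Expected events with uniform accrual and exponential dropout: 372 to 377 at 96 months if 20% drop out by 84 or 96 months, and 357 if 20% drop out by 60 months. At 84 months the same dropout patterns give 317 to 333. So 367 fits the 8-year timeline, not the 7-year one.

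**Gap between Month 60 biopsy and final dose.** With a common stop at month T, completers are followed for T - 24 to T months, so the gap runs from T - 84 to T - 60.
- T = 96: 12 to 36 months; none is within 6 months.
- T = 90: 6 to 30 months; practically none.
- T = 84: 0 to 24 months; 6/24 = 25% of completers, or 26% of event-free completers.

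**Effect on PP2.** Simulation of 600,000 subjects with exponential event times on these inputs. The PP2 rule was applied with last intake as the final dose, and an unstratified Cox model was fitted (Monte Carlo error about 0.01). Assumptions not in the documents: half of early leavers have an exit biopsy, no Month 60 biopsy is missed, and study dropout ends dosing. Deviations and unevaluable Screening biopsies were not modelled. Sizes are scaled to 2000 subjects; the true hazard ratio is 0.62 unless stated.

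| Scenario | PP2 size | With event | Event-free subjects kept | PP2 HR |
|---|---|---|---|---|
| 8 years | 465 | 81% | 5% | 0.89 |
| 8 years, no exit biopsies | 398 | 95% | 1% | 0.94 |
| 8 years, all exit biopsies | 530 | 71% | 10% | 0.87 |
| 8 years, no dropout | 414 | 100% | 0% | 0.97 |
| 8 years, 70% of events found only at biopsy | 396 | 77% | 5% | 0.92 |
| 8 years, 15% miss Month 60, half replaced at end of study | 566 | 66% | 12% | 0.77 |
| 8 years, 15% miss Month 60, all replaced | 664 | 57% | 18% | 0.72 |
| 8 years, 30% miss Month 60, all replaced | 863 | 44% | 30% | 0.67 |
| 7 years | 781 | 43% | 27% | 0.72 |
| 8 years, true HR 1 | 573 | 85% | 6% | 1.00 |
| 8 years, Month 60 biopsy counts whatever dosing follows | 1826 | 21% | 89% | 0.61 |

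The full set gave 0.61 to 0.63 when the true value was 0.62. In the last row, with no exit biopsies, PP2 holds 1760 subjects and the hazard ratio is 0.62.

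**The case against.** **The phrase is undefined.** If last intake means the last dose before the biopsy, a Month 60 biopsy taken on drug qualifies, and there is neither exclusion nor shift. The set's name supports that intention, and in the PK sampling instruction of Protocol 11.3.1.6 the phrase can mean the most recent dose. This stands as a statement of likely intent. But the treatment-emergent and subsequent-event definitions (Protocol Synopsis, SAP Table 5-17) and the follow-up and medication rules (Protocol 9.5) use it for the final dose, and a programmer would probably do the same. If the other meaning is intended, the text still has to say so.

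**The timeline is not settled.** The Synopsis gives 60 months. If every subject stopped at Month 60, the biopsy would qualify. But the same entry makes duration event-driven. With a common stop and 2 years of accrual, 60 months for the last subject enrolled means up to 84 for the first.

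**Some completers stay in.** A reader might infer that all event-free completers are lost. The documents do not support that: Protocol 11.2 provides an end-of-study biopsy for those who missed Month 60, and a 7-year study keeps about a quarter. Nor is every early event admitted, because the Screening-biopsy and deviation conditions still apply.

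**Drug stoppers who remain in follow-up are not modelled.** Protocol 7.1 encourages them to stay. Someone who stops close to Month 60 and has that biopsy qualifies. A subject with an event after Month 24 and more than 6 months after stopping does not. Both paths would lower the share of events in PP2, so the tabulated values are not exact predictions.

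**PP2 is supportive only.** Correct: it carries no alpha, and ITT is also reported.

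**Conclusion.** The point holds for PP2 with last intake read as the final dose. The rule keeps nearly all subjects with events, given an evaluable Screening biopsy and no significant deviation. It excludes event-free completers whose Month 60 biopsy is more than 6 months before their final dose. From about 7.5 years of study duration, that is essentially every event-free completer who had that biopsy.

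With a true hazard ratio of 0.62, PP2 would show roughly 0.7 to 0.95; the extremes run were 0.67 and 0.97. The value depends on study length, exit-biopsy uptake and missed Month 60 biopsies; the documents fix none of these for Part 2.

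A reader might go on to infer that the Part 2 primary result is biased or that a spurious benefit could appear. Neither follows: the primary test uses mITT, and PP2 gives 1.00 when there is no effect. The harm is that a real effect would look much weaker in the supportive analysis.

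**What to change.** Reword the last PP2 criterion in SAP Table 5-1 and Protocol 12.1.1: a biopsy at or after Month 24 qualifies if it was taken on study drug, or no more than 6 months after the last dose preceding that biopsy, whatever dosing follows. In the model this keeps about 1760 to 1826 of 2000 subjects and returns the full-set hazard ratio.

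Do not borrow PP1's minimum-exposure rule. Subjects who reach an outcome leave the study, so such a rule would drop early events because of the outcome. Censoring at a fixed time after last intake is no substitute either, since it changes the estimand.

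Two reconciliations belong with this edit:
- The treatment and follow-up durations in the Protocol Synopsis, Protocol 9.3 and SAP 5.1.2.
- The Part 2 sensitivity row of SAP Table 5-14, which names PP1, whereas that table's time-to-event row and Protocol 12.3.2.2 name PP2.

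The cost is wording in the SAP and a matching protocol clarification before Part 2 unblinding. No new data or procedures are needed.

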5.1.1.1.2 Study Treatments

The following treatment groups are defined for this study:

- Arm A: CVC 150 mg, once daily
- Arm B: Placebo once daily

5.1.1.1.3 Statistical Methodology

The methodologies defined below apply as specified to individual endpoints defined in this SAP. When indicated, 95% two-sided confidence intervals and two-sided p-values will be presented. Individual endpoint analyses may specify exceptions (additions or deletions) to these general definitions.

Table 5-2 Statistical Methodology

Methodology	Description
Categorical descriptive statistics	
 • Number and percentage of subjects in individual categories 
 ○ Subjects with ≥ 1 qualifying event counted once per individual category • N1 if denominator \neq number of subjects in the population (standard percentage denominator) 
 ○ N1 = subjects with non-missing value at corresponding visit
Continuous descriptive statistics	
 • N1, mean, standard deviation (SD), median, minimum, maximum • N1 = subjects with non-missing value
CFB descriptive statistics	
 • Continuous descriptive statistics for baseline, post-baseline, and change from baseline (CFB) values • N1 = subjects with non-missing values at both baseline and the specified post-baseline analysis visit
CFB ANCOVA	
 • Continuous descriptive statistics and standard error (SE) for baseline, post-baseline, and CFB values • Estimates derived from mixed model for CFB value controlling for factors (treatment group, fibrosis stage [2 vs 3], presence or absence of T2DM) and covariate (baseline value) 
 ○ Least squares (LS) means and SEs ○ LS mean differences, SEs, and confidence intervals (CIs) vs Placebo ○ P-values from contrast t-test comparing treatment group vs Placebo • N1 = subjects with non-missing values at both baseline and the specified post-baseline analysis visit
Responder	
 • Categorical descriptive statistics for responders and nonresponders 
 ○ Nonresponders include: 
 ▪ Subjects who do not meet responder criteria ▪ Subjects missing the post-baseline liver biopsy will be included as nonresponders (see Section 5.1.1.1.5 for handling of missing biopsy or inadequate biopsy) • Risk differences and Wilson's method for CIs vs Placebo • Estimates derived from Cochran-Mantel-Haenszel (CMH) model controlling for factors (treatment group, fibrosis stage at baseline [2 vs 3] and presence or absence of T2DM at baseline) 
 ○ Mantel-Haenszel (MH) odds ratios (ORs) and 95% CIs vs Placebo ○ P-values comparing treatment group vs Placebo • N1 = all subjects unless otherwise specified
Time-to-event (TTE)	
 • Categorical descriptive statistics for subjects with events and censoring 
 ○ Censoring includes: 
 ▪ Subjects who do not meet event criteria ▪ Subjects with no post-baseline values of corresponding parameters • Quartiles, estimated event rates, and CIs derived from Kaplan-Meier (KM) nonparametric model using log-log transformation of survival function using product-limit method • Estimates derived from Cox proportional hazards model controlling for factors (treatment group, fibrosis stage at baseline [2 vs 3] and presence or absence of T2DM at baseline) 
 ○ Hazard ratios (HRs) and CIs vs Placebo • Estimates derived from stratified log-rank model controlling for factors (treatment group, fibrosis stage at baseline [2 vs 3] and presence or absence of T2DM at baseline) 
 ○ P-values comparing treatment group vs Placebo • N1 = all subjects unless otherwise specified

Methodology	Description
KM figure	
 Step-function figure of cumulative distribution function [1 - survival function] estimates with censoring indicators, derived from KM nonparametric model

CFB = change from baseline; ANCOVA = analysis of covariance; TTE = time-to-event.

Raw and derived data listings will be provided, and will be fully defined in the table, figure, and data listing specification document.

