Subjects who progress to cirrhosis or reach an adjudicated liver-related clinical outcome will complete the study and return to the clinic for a Follow-up visit (Visit 98) 30 days after the last dose of study drug. After completion of the Follow-up visit (Visit 98), subjects will become eligible for open-label access to CVC in a separate study (Clinical Study Protocol 3152-201-002).

Part 1

At Baseline (Day 1), eligible subjects will be assigned to the treatment arms using permuted block randomization stratified by NASH CRN fibrosis stage (2 or 3) and presence or absence of documented type 2 diabetes mellitus (T2DM) (yes or no). Eligible subjects will be randomized 2:1 to one of the following 2 treatment arms:

Arm	N	Treatment
A	800	CVC 150 mg, once daily
B	400	Placebo, once daily

All subjects will undergo safety assessments at the Baseline visit and at Months 1, 3, 6, 9, and 12. The liver biopsy, used to evaluate the efficacy endpoints, must be performed within ± 2 weeks of the Month 12 visit (Visit 7).

Part 2

In Part 2, Baseline (Day 1) eligible subjects will be randomized to treatment using permuted block randomization, stratified by presence or absence of documented T2DM (yes or no). Newly enrolled subjects will be randomized 2:1 to one of the following 2 treatment arms to achieve a total of approximately 2000 randomized subjects in Part 2 (of which approximately 1200 subjects will have been randomized in Part 1):

Arm	Newly Randomized Subjects in Part 2 N	Total Subjects (Randomized in Part 1 or Part 2) N	Treatment
A	534	1334	CVC 150 mg, once daily
B	266	666	Placebo, once daily

Subjects who enter Part 2 from Part 1 of the study will have study visits every 3 months until Part 2 is completed. Study drug will be dispensed and adverse events (AEs), concomitant medications, and adherence to study drug will be reviewed at every visit (every 3 months). Safety laboratory assessments will be performed every 6 months through the end of the study.

Subjects who are randomized in Part 2 and who did not participate in Part 1 of the study will undergo safety laboratory assessments at Months 1, 6, and 12 and every 6 months thereafter through the end of the study. Beginning at Month 3, AEs, concomitant medications, and adherence will be reviewed every 3 months through the end of the study.

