5.1.1.1.4 Estimands

Estimands for Global Part 1 primary, key secondary, and secondary endpoints are provided below:

Table 5-3 Estimand Language

Endpoint: Global Part 1	Estimand Language
Primary	
 Population: All randomized subjects with NASH CRN fibrosis stage 2 or 3 who also met inclusion and exclusion criteria for the study. The analysis population is the modified ITT population. Variable/Endpoint: Improvement in fibrosis by at least 1 stage (NASH CRN system) AND no worsening of steatohepatitis (no worsening of lobular inflammation or hepatocellular ballooning grade 2005) on liver histology at Month 12 relative to Screening biopsy Intercurrent Event: Hypothetically envisage that those who withdraw from the study prior to the liver biopsy at Month 12 or those who do not have readable liver biopsies at the Month 12 visit assessment will be considered as non-responders (those who do not improve in fibrosis stage). Population-level Summary: Difference in responder rates from screening biopsy for fibrosis stage improvement (with no worsening of steatohepatitis) at Month 12 between the CVC group versus the placebo group using the Cochran-Mantel-Haenszel (CMH) test, stratified by NASH CRN fibrosis stage (2 vs 3) and T2DM at baseline (presence vs absence)
Key Secondary	
 Population: All randomized subjects with NASH CRN fibrosis stage 2 or 3 who also met inclusion and exclusion criteria for the study. The analysis population is the modified ITT population. Variable/Endpoint: Improvement in fibrosis by at least 2 stages (NASH CRN system) AND no worsening of steatohepatitis (no worsening of lobular inflammation or hepatocellular ballooning grade 2005) on liver histology at Month 12 relative to Screening biopsy Intercurrent Event: Hypothetically envisage that those who withdraw from the study prior to the liver biopsy at Month 12 or those who do not have readable liver biopsies at the Month 12 visit assessment will be considered as non-responders (those who do not improve in fibrosis stage). Population-level Summary: Difference in responder rates from screening biopsy for fibrosis stage improvement (with no worsening of steatohepatitis) at Month 12 between the CVC group versus the placebo group using the Cochran-Mantel-Haenszel (CMH) test, stratified by NASH CRN fibrosis stage (2 vs 3) and T2DM at baseline (presence vs absence)

Endpoint: Global Part 1	Estimand Language

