- Region-specific Europe: Part 1 testing is only for the region-specific primary endpoint, a binary endpoint. The surrogate endpoint will be tested at the 0.0012 (2-sided) alpha level to manifest strong evidence from a single confirmatory study, and 0.048 (2-sided) level for study success.

The general description of the domains of clinically-related endpoints is stated below.

Table 5-14 Domain 1 Analyses

Type of Endpoint	Description	Timing	Methodology
Part 1: Primary efficacy endpoint (binary)	
For the primary efficacy analysis in Part 1, using the mITT analysis set, any available liver biopsy after baseline will be used as the Month 12 biopsy, no matter when it was obtained relative to the first dose of study drug. Subjects who do not have an evaluable liver biopsy at both Screening and Month 12 will be included in the analyses as nonresponders. Subjects with multiple liver biopsies will have the evaluable biopsy closest to the Month 12 visit included in the analysis.
 
The proportion of subjects who meet the primary efficacy endpoint in Part 1, and the proportion who meet each component of the primary efficacy endpoint, will be summarized by treatment group. Two-sided 95% CIs for the proportion of subjects who meet the primary efficacy endpoint, calculated using Wilson's method for CI, will be reported.
 
Analysis of the primary and key secondary endpoints of Part 1 will use the Cochran-Mantel-Haenszel (CMH) test, stratified by true fibrosis stage (2, 3) and T2DM status (presence, absence) at baseline, for a total of 4 strata, to compare the rates in the 2 randomized treatment arms.
	
Screening, Month 12
 
The primary analysis of Part 1 will occur when approximately 1200 randomized subjects have been followed for at least 12 months. Subjects who will contribute to the primary analysis of Part 1 will be identified before unblinding of any subjects for Part 1 analysis; subjects who will not contribute to the primary analysis of Part 1 will be identified by date of randomization. Individual subjects' treatment group assignments will not be disseminated to the sites until the end of Part 2 to allow for continued blinded assessment during Part 2.
	
Responder
 
Two-sided 95% CIs for responder using Wilson's method for CI.
 
Cochran-Mantel-Haenszel (CMH) test, stratified by true fibrosis stage (2, 3) and T2DM status (presence, absence) at baseline

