6.1 Study Treatment Conventions

Treatment assignment will be done using permuted block randomization via IxRS stratified by NASH CRN fibrosis stage (2 or 3) and presence or absence of documented T2DM (yes or no). In case of discordance of the assignment of randomization strata between IxRS and EDC, the true fibrosis stage and T2DM status at baseline will be used for the analysis.

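### The Part 1 responder estimand is a rate difference tested with a stratified CMH test, but the SAP specifies no stratified estimate of that difference (minor: clarity and precision, not bias)

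*SAP*

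**What the plan says.** SAP 5.1.1.1.4 (Table 5-3) gives the population-level summary for the Part 1 primary estimand as "Difference in responder rates from screening biopsy for fibrosis stage improvement (with no worsening of steatohepatitis) at Month 12" between the arms, using a CMH test stratified by fibrosis stage and T2DM. The key secondary and secondary responder estimands also use a rate difference. The EU primary estimand is the Global key secondary one, so it is covered too.

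SAP 5.1.1.1.3 (Table 5-2, Responder row) lists "Risk differences and Wilson's method for CIs vs Placebo" as a bullet of its own. The next bullet controls for treatment, stage and T2DM. It yields "Mantel-Haenszel (MH) odds ratios (ORs) and 95% CIs vs Placebo" and the p-values.

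SAP Table 5-14 describes the primary CMH test as "stratified by true fibrosis stage (2, 3) and T2DM status (presence, absence) at baseline, for a total of 4 strata". Its Wilson interval is for single proportions: "Two-sided 95% CIs for the proportion of subjects who meet the primary efficacy endpoint". It adds no stratified difference. Where the randomisation system and the clinical database disagree, SAP 6.1 says that "the true fibrosis stage and T2DM status at baseline will be used for the analysis".

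**The concern.** The estimand, the estimator and the test should line up. Here the test is stratified, the stratified estimate is an odds ratio, and the rate difference that the estimand names has no stated strata, weights or variance. Wilson's method is an interval for one proportion. An interval for a difference needs a further choice, such as Newcombe's combination of the two Wilson intervals, so two programmers could produce different intervals from the same line.

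Three things are at stake: a little precision; adjustment for any imbalance within the strata as analysed; and a choice about the main effect estimate that might otherwise be made after unblinding. The gap reaches both the Global and the EU primary results.

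**Working it through.** **Inputs from the documents.** Part 1 planned 800 vs 400, 25% vs 15%, two-sided alpha 0.0012 and 0.048 (SAP 5.1.2, 5.1.1.3.1). Randomisation is 2:1 in permuted blocks within four strata (SAP 4.1.1). Part 1 actually randomised 1293; the totals less the newly randomised numbers in SAP 5.2.1 imply 1334 − 472 = 862 and 666 − 235 = 431.

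**Assumptions, not in the documents.** Stratum shares 20/20/30/30%; placebo rates as listed below; the same risk difference in every stratum.

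**1. The plan's own figure.** Unpooled standard error = √(0.25×0.75/800 + 0.15×0.85/400) = 0.02352. Power = Φ(0.10/0.02352 − 3.239) = Φ(1.013) = 84.4%, against 84% stated. The same formula gives 97.4% for the key secondary endpoint, against 97% stated. So the inputs are read correctly. (A pooled null variance, closer to what CMH uses, gives 78.2% and 89.1%; that is a separate matter.)

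**2. What the crude line yields at plan.** For 200/800 vs 60/400 the difference is 0.100. The Newcombe interval is 0.052 to 0.144 at 95% and 0.019 to 0.172 at 99.88%, the level that matches alpha 0.0012.

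**3. Precision, by formula.** With 862 vs 431 and placebo rates 5/10/18/22% (CVC 10 points higher), the overall rates are 15% and 25%.
- Crude variance: 0.15×0.85/431 + 0.25×0.75/862 = 0.000513.
- Within-stratum variance: the weighted mean of p(1−p) is 0.12326 on placebo and 0.18326 on CVC, so 0.12326/431 + 0.18326/862 = 0.000499.
- Ratio 0.971; √0.971 = 0.986, so the interval is about 1.4% narrower.

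**4. Precision, by simulation.** At 800/400, exact 2:1 in each stratum and a true difference of 10 points, the crude and Mantel-Haenszel (MH) differences are identical. Mean 95% interval widths, with the Sato variance for MH:

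| Placebo rates | Crude | MH | Narrower by |
|---|---|---|---|
| 15% in all | 0.0922 | 0.0920 | 0.2% |
| 20/16/14/12% | 0.0922 | 0.0918 | 0.4% |
| 30/20/10/6% | 0.0918 | 0.0891 | 3.0% |

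A stratified Newcombe interval gave essentially no narrowing.

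**5. Imbalance.** With free chance imbalance across strata (an upper bound, since randomisation is stratified), the crude and MH differences differ with an SD of 0.1 to 0.6 points. In 97.5% of trials they differ by no more than 0.3 to 1.3 points, depending on the assumed rates.

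**6. Disagreement with the CMH p-value at matched alpha, balanced strata.**

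| True difference | Alpha | Crude interval | MH (Sato) interval |
|---|---|---|---|
| 10 points | 0.05 | 0.0–0.2% | 0.1–0.3% |
| 10 points | 0.0012 | 0.4–2.8% | 4.3–4.7% |
| 5 points | 0.05 | 0.2–2.5% | 2.6–2.9% |
| 5 points | 0.0012 | 0.3–2.4% | 4.7–4.9% |

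Under free imbalance the crude figure rises to as much as 8.1% (5 points, alpha 0.05) and 6.0% (10 points, alpha 0.0012). In the first of these cases a stratified interval brings it down to low single digits. At alpha 0.0012 the stratified Newcombe interval follows the CMH test more closely than MH with the Sato variance.

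**7. Interval level.** A 95% interval excludes zero while the CMH p-value is 0.0012 or more in 17 to 20% of trials at 10 points and 44 to 45% at 5 points. This is far larger than anything in step 6.

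**The case against.** The strongest reply is that the SAP nowhere calls the difference unstratified. That reading comes from silence and from where the bullet sits. Table 5-3 ties the difference to the stratified CMH test, and the detailed table specifications are in a separate document that is not available here. This stands as a limit on the claim: what can be said is that no stratified difference is specified. It does not remove the gap. Elsewhere in Table 5-2 the effect estimates (least-squares mean differences, hazard ratios) sit under the adjusted model, and the responder difference does not.

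A reader might infer three stronger things, none of which the documents support.
- *That the reported effect ignores the randomisation strata.* A stratified odds ratio with its interval is also planned, and so is a logistic regression with stage and T2DM as predictors.
- *That the difference is biased.* Blocked 2:1 allocation within strata makes the crude difference a valid estimate of the marginal rate difference. Imbalance in the strata as analysed depends on discordance between the two systems, whose frequency the documents do not give.
- *That stratifying makes estimate and test agree.* Step 6 shows otherwise: with balanced strata and alpha 0.0012, the MH interval with the Sato variance disagrees with CMH more often than the crude one does.

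**Conclusion.** The point holds in limited form. The Part 1 responder estimands are rate differences, and the SAP supplies no stratified estimator for them, although it randomises and tests within the same four strata. The consequence is minor: an interval about 1 to 3% too wide if strata differ appreciably in response and almost none if they do not, no adjustment for imbalance in the true strata, and an interval method open to more than one reading. Validity is not in question. The sizes rest on the assumed stratum shares and rates and a constant risk difference. The mismatch between 95% intervals and a 0.0012 test is larger than any effect of stratification, and stratifying does not cure it.

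**What to change.** In Table 5-2, with a cross-reference in Table 5-14:

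1. Name the Mantel-Haenszel weighted risk difference over the same four strata as the estimate for the primary, key secondary and secondary responder endpoints.
2. Name one stratified interval. MH with the Sato variance gives the small precision gain. Stratified Newcombe gives essentially none, but follows the CMH test more closely at alpha 0.0012 and may suit the sparse endpoints of improvement by two or more stages. At 2.2% of 431, only about 9 placebo responders would be spread over four strata; neither interval has been checked there, so check before choosing.
3. Keep the per-arm Wilson intervals as description and the odds ratio as supportive.
4. State the interval level for each alpha: 99.88% with 0.0012 and 95.2% with 0.048, next to the conventional 95%.
5. Do not claim that interval and p-value will always agree.

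The cost is a few SAP lines before Part 1 unblinding and standard software options. No extra data are needed, and the test and alpha are unchanged.
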